The goal of this proposal is to conduct a prospective randomized controlled phase III study comparing Rituximab (RTX) to Cyclosporine (CSA) in the treatment of patients with IMN. Once a patient with IMN and proteinuria $\geq 5\text{g}/24\text{h}$ is identified, meets other entry criteria and consents to the study, he/she will receive a minimum of 3 months of conservative therapy aimed at maximizing Angiotensin II blockade (run-in phase). If at the end of this period the patient still meets entry criteria he/she will be randomized into a 12-month treatment period, and a subsequent follow-up of 12 months. Efficacy of treatment will be assessed by remission status (based on changes in proteinuria) at 24 months from randomization. Patient safety will be assessed via collection of adverse event data and evaluation of pre- and post-treatment laboratory data. At the 6-month post-randomization visit, patients who have been randomized to either CSA or RTX but who do not have a reduction in proteinuria $\geq 25\%$ (confirmed on repeat measurements within 2 weeks) will be considered treatment failures and exit the study. Data from that point onward will be censored. Patients in the RTX group who have a reduction in proteinuria of equal to or $>25\%$ at 6 months will be given another identical course of RTX (1g x 2). This treatment regimen was chosen given our initial data that suggested a percentage of our cohort appeared to respond to an additional course of therapy. Data from our 2 pilot studies showed that RTX is out of the circulation by month 2 in the majority of patients and B cells have recovered by month 3 in patients treated with RTX 1g x 2 (the regimen chosen for the study). Thus, at 6 months, patients in the RTX arm are completely, at least as best as we can measure, free of immunosuppression, and hence the second course should not be associated with additive toxicity. The same definition of response will apply to the CSA arm at 6 months. An equal to or $>25\%$ reduction in proteinuria will dictate continuation of the CSA for an additional 6 months (total of 12 months of full dose CSA). This assessment at six months allows a balance between risk-benefit in both arms. The protocol provides similar exposure to immunosuppression in both arms and allows an early exit for patients related to safety issues by providing a lack of efficacy (futility) end point at 6 months.

Primary endpoint

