Rituximab: Patients randomized to the RTX arm will receive 1000 mg IV on Days 1 and 15. Patients who achieve complete remission at 6 months will not be retreated. A second course of RTX 1000 mg IV will be administered at study month 6 for individuals who have not achieved a complete remission, but have achieved at least a $\geq 25\%$ reduction compared to their central laboratory (Mayo Clinic Rochester) baseline (Time 0) proteinuria (but not a CR). Dosing at study month 6 will be independent of CD19/20+ B cell count. The rationale for retreating patients who have had an equal to or $> 25\%$ reduction in proteinuria at 6 months is based on our experience in our pilot studies (first study using 1000 mg on Days 1 and 15 and second study using 4 weekly doses of $375\text{mg}/\text{m}^2$) where an increase in the proteinuria remission rate was achieved after a second course of treatment. In our 2 studies repeated courses of RTX were not associated with additive adverse effects in comparison to their first course. If after six months the reduction in proteinuria is less than 25% compared to baseline the RTX treatment will not be repeated, the patient will exit from the study and will be considered a failure of therapy.

Dosage and Administration of Rituximab: The first infusion of both courses (Day 1 and Day 181) of RTX will be administered IV at an initial rate of 50 mg/hr. All patients

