CSA was 175 ng/ml the goal would be to reduce it to 130 ng/ml by reducing the dose by approximately 25% - dose reduction is approximate because CSA is only available in specific dose strengths (25mg, 100mg) and therefore some rounding may be required). If with this dose reduction the creatinine does not return to within 30% of baseline levels within 3 weeks, then a second dose reduction of approximately 25% with a similar reduction in CSA trough level (e.g. if CSA trough level was 100 ng/ml, reduce to 75 ng/ml) will be used. If the creatinine does not fall to within 30% of baseline values with this second dose reduction, the drug will be discontinued. If after six months the reduction in proteinuria is less than 25% compared to baseline the drug will be discontinued, the patient will exit from the study and be considered a failure of therapy. At the end of 12 months, Cyclosporine will be tapered by 1/3 of the maintenance dose monthly and hence discontinued after 2 months. Serum potassium and serum creatinine levels will be checked at the initiation of Cyclosporine in conjunction with blood draw for CSA level. If Cyclosporine dose is changed during treatment, potassium, creatinine and CSA levels will be rechecked every two weeks +/- 3 days post increase/decrease in CSA dosage until levels are stable and at target.

[figure not shown]

Figure 4. Schematic representation of the study design.

Blinding

This will be an open-label study with neither patients nor physicians blinded. Blinding, for this study, was considered difficult and unnecessary and would significantly add to the cost of the study. The need to provide RTX intravenously would require that the CSA arm patients would have to receive an IV infusion of saline which seems unjustifiable from the scientific and budgetary points of view. Furthermore, with the exception of

quality of life measures, all endpoints are based on objective (laboratory) criteria. Having the physicians in the study blinded to CSA level also introduces a potential risk factor that's unnecessary in our estimation. Documentation of cyclosporine levels will ensure that patients are taking the drug at the appropriate time and achieving the prescribed levels indicated in the protocol.

Pharmaceutical logistics

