For those patients in the Cyclosporine arm, **Cyclosporine trough level measurements will be done every 2 weeks +/- 3 days after initiation of Cyclosporine until levels are stable and at target. Potassium and creatinine will also be checked in conjunction with CSA level. If Cyclosporine dose is changed during treatment, potassium, creatinine and CSA level will be rechecked every 2 weeks +/- 3 days until levels are stable and at target.** Cyclosporine levels will also be assessed whenever serum creatinine rises by $>30\%$ without a recognizable reason such as volume depletion, additional drugs, sepsis, etc. Patients who cannot tolerate the medications and/or who are treatment failures at 6 months will exit the study at 6 months (i.e., the 6 month visit and accompanying data collection should still occur). Patients who go in to complete remission will discontinue study drug but will continue with full visit follow-ups until month 24 as scheduled. However, the therapeutic/management plan for these patients will be solely at the discretion of the managing nephrologist although while in CR no further immunosuppressive therapy is recommended. Likewise, patients who relapse from either a partial or complete remission or who are not in partial or complete remission by the end of the treatment period (i.e., 12 months) will continue with the visit schedule, but the therapeutic/management plan will be solely at the discretion of the managing nephrologist. Finally, for patients who temporarily stop taking Cyclosporine, there are three possible scenarios:

1. Patients who discontinue Cyclosporine for < 2 weeks may simply be restarted on the study drug and continue to fully participate in the trial. The treatment is to be restarted at its former dose and the patient returned to the regularly scheduled follow-ups including the periodic sampling for assessing potassium, creatinine and CSA trough levels.
2. Patients who discontinue Cyclosporine for ≥ 2 weeks, but < 4 weeks may also be restarted on the study drug at its former dose and fully participate in the trial, but the temporary discontinuance will be logged as a protocol deviation and the missed treatment days will be made up at the end of month 12. This is to ensure that all patients receive approximately 12 months of treatment with study drug.

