3. Patients who discontinue Cyclosporine for ≥ 4 weeks will not be restarted on study drug, but will continue with full visit follow-ups until month 24 as scheduled. The therapeutic/management plan will be solely at the discretion of the managing nephrologist.

Laboratory testing

In order to contain costs all clinical tests will be carried out locally at the recruiting centers. However, at critical time points: Time 0, and 6, 12, 18, and 24 months from start of treatment, recruiting centers will ship to Mayo Clinic, Rochester, Minnesota, 2 blood samples and 2 urine samples (aliquots obtained from two 24h urine collections) for determination of serum creatinines, serum albumins and urinary protein/creatinine ratios. Blood and urine kits will be provided by Mayo Clinic, Rochester, Minnesota, for these

samples along with shipping costs (see Lab Manual). The Central Lab results (Mayo Clinic, Rochester, MN) will be used for statistical purposes since this will ensure a standard methodology is applied to the critical (for the trial analysis) laboratory assessments. By measuring the volume of the 24-hour urine collection we will also be able to calculate both clearance and the 24-hour urine protein from the aliquot. Proteinuria results at Time 0, 6, 12, 18 and 24 months will be taken as the mean of two 24-hour urine collections done back to back (within 14 days of each other), and the mean of these 2 collections will be used to determine CR, PR, or NR.

In order to control for the possibility of under collection or over collection of urine, a maximum 20% variation in total 24h urine creatinine (mg/specimen) will be allowed between the two urine collections required at Time 0, 6 months, 12 months, 18 months, and 24 months. A difference of greater than 20% will necessitate a third urine collection (also to be sent to the central lab), with the values from one of the two previous collections being discarded. We will use the subject's weight to approximate the expected total urine creatinine (mg/kg) to determine which of the previous collections is closest to the truth and which should be discarded. It is anticipated that a 3rd urine collection will be needed in <10% of cases. Proteinuria will be calculated as the mean of these two 24-hour urine collections.

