After the second course of RTX therapy at six months they will have no further RTX therapy regardless of their proteinuria level
3. Significant potential life threatening infection.
4. Persistent elevation of liver enzymes >2 x normal (despite CSA arm dose reduction).
5. Persistent elevation of serum potassium >6.0 mEq/l despite diet changes, ACEi/ARB reduction, diuretic dose increase (and in the CSA arm dose reduction).
6. A rise in serum creatinine by $>30\%$ above baseline that persists in the absence of secondary causes such as volume depletion or use of potential nephrotoxic agents (and despite adjustments in the CSA dose)
7. Persistent hypertension in either arm, i.e. supine blood pressure >160 mmHg systolic or >90 mmHg diastolic, despite institution of maximum antihypertensive therapy (and despite adjustments of CSA dose)

8. Other clinically relevant adverse effects not resolved by reduction in dosage of test medications.
9. Development of any malignancy or lymphoproliferative disorder.
10. Pregnancy.
11. The appearance of an independent disease whose standard therapy requires continuous administration of significant amounts of corticosteroids, other immunosuppressive agents or plasma exchange therapy.
12. Serious concomitant disease with an expected survival of less than 4 years.
13. At the wish of the patient.
14. The study will be placed on hold if 3 of the first 5 patients enrolled and treated with RTX or CSA develop severe opportunistic infections, or experience Grade 3-4 SAEs.

Patients who choose to discontinue study medication or are withdrawn because of adverse events will be strongly encouraged to continue follow up examination to the study termination.

Ancillary studies:

1. DNA Testing

Recent data show that in patients with membranous nephropathy, mutations in HLA-DQA1 and PLA2R1 alleles are associated with an increased risk for developing membranous nephropathy.⁸⁰ One of these alleles, the PLA2R1, is in fact the gene for the PLA2 receptor. In our pilot studies, ~70% of the patients with membranous nephropathy had antibodies present in circulation against PLA2 receptor.⁷⁷ Thus we would like to evaluate a linkage between the presence of these antibodies and potential genetic mutations in this group of patients. We will ask for the patients consent to further evaluate this linkage by collecting samples of blood to perform additional testing as part of their informed consent form (ICF).

2. Quantitative gene expression analysis

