Adverse events (both patient and event counts) will be tabulated by body system, severity and, for each severity, by investigator-assessed relationship to study drug. Group comparisons for adverse events with 4 or more occurrences will be done using chi-square or Fisher's exact test. The last RTX injection is at 6 months and the tapering of Cyclosporine will be completed by the end of month 14. Hence, the adverse events analyses will focus on events through month 18, allowing these additional months for potential lingering Cyclosporine or RTX complications.

The analysis of the primary endpoint (urine protein failure at month 24) will be intent-to-treat (ITT), and will include all randomized subjects in the analysis. For those without a 24 month visit, the 18 month visit results will be used if available, otherwise they will be assumed to have failed at 24 months. Per protocol (PP) analyses will also be done including only those subjects who receive a full course of study medication and who have a 24 month visit.

Interim analyses: No interim analyses for efficacy will be performed during the trial, however safety data will be compiled and reviewed approximately every six months or at the request of the Data and Safety Monitoring Board.

Investigator and Coordinator Training: In order to make efficient use of funding, annual investigator and coordinator meetings will be coordinated with national nephrology meetings where possible. It is expected that the majority of the training will occur through web-based technology and will be coordinated through the data management and coordinating Center.

The **Data Management and Coordinating Center (DMCC)** is located at the Applied Health Research Center (AHRC) at St. Michael's Hospital/University of Toronto. The DMCC will be responsible for facilitating all aspects of the study planning, training, implementation, data collection and analysis.

The clinical information collected for this study will be stored at the DMCC at the Applied Health Research Centre of St. Michael's Hospital in Toronto, ON, Canada and also sent to a federal data repository held by the Office of Rare Diseases Research (ORDR) and located at the University of South Florida (USF) in Tampa, FL.

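### The per-protocol set excludes every patient the protocol itself exits as a month-6 failure, so it is partly selected on an efficacy outcome

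*Combined protocol and SAP*

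**What the plan says.** The Statistical and Analytical Plan names two analysis sets for the primary endpoint, remission (complete or partial) at 24 months. ITT takes all randomized patients. When the month-24 visit is missing, "the 18 month visit results will be used if available, otherwise they will be assumed to have failed at 24 months". PP is a further analysis "including only those subjects who receive a full course of study medication and who have a 24 month visit".

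The exit rule appears in four places and applies to both arms. Patients without a 25% proteinuria reduction at month 6 "will be considered treatment failures and exit the study" (Overall Research Design and Methods). For rituximab (RTX), "the RTX treatment will not be repeated, the patient will exit from the study and will be considered a failure of therapy". For cyclosporine (CSA), "the drug will be discontinued, the patient will exit from the study and be considered a failure of therapy". Patient monitoring and evaluation confirms the timing: patients "who are treatment failures at 6 months will exit the study at 6 months".

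Other patients stop drug but can still reach month 24. Those off CSA for four weeks or more "will not be restarted on study drug, but will continue with full visit follow-ups until month 24 as scheduled". Those who stop by choice or because of adverse events "will be strongly encouraged to continue follow up examination to the study termination" (Stopping points for medications). Neither provision covers month-6 failures.

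**The concern.** A PP set is meant to show the result among patients treated as the protocol intends. The month-6 failures were treated as intended: the protocol told them to stop and leave. They drop out of PP because of their proteinuria after randomization, which is the variable behind the primary endpoint. That is selection on an early efficacy result.

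PP also drops patients for ordinary reasons: an incomplete course, or a month-18 result standing in for month 24. The PP estimate combines both kinds of exclusion.

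In a non-inferiority trial, readers compare PP with ITT to see whether poor adherence or missing data shaped the conclusion. PP is the only other set named for the primary endpoint, and as defined it does not answer that question cleanly. It also favours whichever arm has more early failures.

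**Working it through.** **Inputs from the Sample size estimation paragraph.** Remission at 24 months 55% (RTX) and 45% (CSA); margin 15 points; one-sided alpha 0.025; power 80%; 63 per arm.

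**The plan's own figure.** n = (0.55×0.45 + 0.45×0.55) × (1.960 + 0.842)² / (0.10 + 0.15)² = 62.2, rounded up to 63. This reproduces. Power at 63 per arm is 80.5%.

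**Who is in each set.** A month-6 failure has no month-18 or month-24 result, so ITT counts a failure. PP requires a month-24 visit, so the patient is absent however a full course is read. No section restores these patients.

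**Formulas.** For each arm let p be the ITT remission rate, e the share exiting at month 6 (all ITT failures), and x the share of randomized patients who are ITT responders but leave PP for another reason.

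- PP rate = (p − x) / (1 − e − x)
- PP n = 63 × (1 − e − x)
- Chance of meeting the margin = Φ[(d + 0.15)/SE − 1.96], where d is the PP difference RTX minus CSA and SE is unpooled

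The documents give no month-6 exit rates, so every e and x below is an assumption. The percentages are the chance that the supportive PP analysis would meet the 15-point margin. They are not error rates of the trial.

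**1. Planning rates, 55% versus 45%, no other exclusions (x = 0)**

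| Exits RTX/CSA | PP rates | Difference | Chance of meeting margin |
|---|---|---|---|
| 0/0 (same as ITT) | 55.0% vs 45.0% | +10.0 | 80.5% |
| 20%/20% | 68.8% vs 56.3% | +12.5 | 82.0% |
| 25%/25% | 73.3% vs 60.0% | +13.3 | 83.9% |
| 25%/20% | 73.3% vs 56.3% | +17.1 | 92% |
| 20%/25% | 68.8% vs 60.0% | +8.8 | 69% |
| 30%/20% | 78.6% vs 56.3% | +22.3 | 97.9% |
| 20%/30% | 68.8% vs 64.3% | +4.5 | 51.6% |

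With equal exits the difference is simply divided by 1 − e (0.10/0.80 = 0.125), so the shift is small. It becomes large when the arms differ.

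**2. Truth at the margin, 30% versus 45%, x = 0**

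| Exits RTX/CSA | PP rates | Difference | Chance of meeting margin |
|---|---|---|---|
| 0/0 (same as ITT) | 30.0% vs 45.0% | −15.0 | 2.5% |
| 25%/25% | 40.0% vs 60.0% | −20.0 | 0.7% |
| 30%/20% | 42.9% vs 56.3% | −13.4 | 3.6% |
| 40%/20% (extreme) | 50.0% vs 56.3% | −6.3 | 12.6% |

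**3. Mixing of sources, planning rates.** Suppose 5% of CSA patients are ITT responders dropped for an incomplete course (x = 0.05 in CSA, 0 in RTX).

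- No month-6 exits: 0.550 versus 0.40/0.95 = 0.421, difference +12.9 points.
- 20%/20% exits as well: 0.6875 versus 0.40/0.75 = 0.533, difference +15.4 points, 87.6%.

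The first result is almost the +12.5 points that 20%/20% exits give with perfect adherence.

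Simulation with random exit counts agreed with the approximations to within about one point.

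**The case against.** ITT is primary, PP carries no decision rule, and the plan specifies no margin test on PP. The large shifts need unequal exits, which are assumed. The sample size paragraph describes 12-month remission on RTX as close to that on calcineurin inhibitors, which leans towards similar exits. With equal exits the shift is 2 to 3 points, and when the truth lies at the margin PP becomes stricter. The ancillary remission cohort section expects 70% of randomized patients in remission at the end of treatment, so pooled exits should not exceed about 30%; the 40%/20% case sits at that ceiling. The month-6 visit still takes place for these patients, so exits by arm will be known and could be added back. Finally, dropping patients who stop drug or miss month 24 is what a PP set normally does.

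Most of this stands, and it limits the size of the point. It does not remove it. A 12-month remission rate is not a month-6 exit rate, and Preliminary Studies says the fall in proteinuria after RTX is gradual, so equal exits cannot be presumed. A 5-point imbalance already moves the PP difference to +17.1 or +8.8. That the exits can be added back later is a reason to write the rule now. The ordinary exclusions are not a fault in themselves; they matter here because the single PP estimate does not separate them from the month-6 failures.

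One side issue also stands. Patient monitoring and evaluation exits patients who cannot tolerate the drugs at month 6, while Stopping points for medications encourages those withdrawn for adverse events to stay in follow-up. These passages must be reconciled, because they determine who can have a month-24 visit.

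**Conclusion.** The concern holds. As written, PP removes protocol-compliant month-6 failures on the basis of a post-randomization efficacy result, so its difference from ITT cannot be read as the effect of non-adherence. The primary ITT analysis, the sample size and the formal conclusion are untouched. Direction and size are unknown because exit rates by arm are not given. On the assumed rates, the planning difference of +10 points becomes +12.5 to +13.3 with equal exits of 20% to 25%, and anywhere from +4.5 to +22.3 when the arms differ by 10 points. This should be corrected, but it does not threaten the trial's main result.

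A smaller gap goes with it: a full course is not defined for patients in complete remission at month 6, who receive a shorter course as directed. The plan expects few of them.

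**What to change.** Rewrite the PP definition in the Statistical and Analytical Plan:

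- Define PP by adherence to the assigned regimen as the protocol directs, including directed stopping at month 6.
- Keep month-6 treatment failures who were treated as directed up to that point. Count them as failures and exempt them from the month-24 visit condition.
- State that month-6 complete remitters treated as directed satisfy the full-course condition and enter with their month-24 status.
- State how patients who stop for intolerance are classified, once the two follow-up passages agree.

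With other exclusions set aside, this removes the exit-driven shift: at the planning rates PP returns to +10 points and 80.5%. The cost is one paragraph of analysis wording, with no extra data, visits or patients and no change to treatment. The one drawback is that PP remission rates will be lower than those among completers.
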